1.6 Compliance Statement

This study will be conducted in full accordance all applicable Children's Hospital of Philadelphia Research Policies and Procedures and all applicable Federal and state laws and regulations including 45 CFR 46, and the Good Clinical Practice: Consolidated Guideline approved by the International Conference on Harmonization (ICH) and all relevant FDA regulations. All episodes of noncompliance will be documented.

The investigators will perform the study in accordance with this protocol, will obtain consent and assent, and will report unanticipated problems involving risks to subjects or others in accordance with The Children's Hospital of Philadelphia IRB Policies and Procedures and all federal requirements. Collection, recording, and reporting of data will be accurate and will ensure the privacy, health, and welfare of research subjects during and after the study.

2 STUDY OBJECTIVES

The purpose of the study is to determine if dupilumab can allow introduction of EoE triggered foods to be added reintroduced back into the diet without causing exacerbation of disease.

2.1 Primary Aim

- 1) Evaluate the efficacy of Dupilumab, a humanized anti-IL4 receptor alpha monoclonal antibody, to allow successful food introduction into diet
- 2) Assess changes in clinical (symptoms, QOL) and biologic parameters after food introduction.

The secondary Endpoint:

- Maintenance of resolution (<15 eosinophils/HPF on peak measurements) of eosinophilia observed on esophageal biopsies
- Maintenance of remission (<6 eosinophils/HPF on peak measurements)
- Change in mean esophageal eosinophil count from baseline to the end of treatment.
- Change in symptoms scores at the end of treatment compared to baseline
- Interval change on a validated endoscopic scoring system, EREFS
- Interval change on esophageal compliance and distensibility measured by EndoFlip
- Interval change in mRNA transcriptome profile (esophageal tissue), Th2 phenotype (peripheral blood), blood eosinophilia, and total serum IgE.

- Change in the Eosinophilic Esophagitis Quality of Life Score from baseline to the end of treatment

3 INVESTIGATIONAL PLAN

3.1 General Schema of Study Design

This study is an open label exploratory study to examine if patients controlled with dupilumab can successfully introduce EoE trigger foods back into their diet.

In the initial 12-week period, patients will start on dupilumab on the doses used in the phase 3 trials to control disease. If disease is controlled based on histologic and symptom control at week 12 endoscopy, patients will start on EoE trigger food. The trigger foods will be based on both a combination of history and histology results. The food will have triggered EoE by histology in the last 2 years and symptoms in the last year when reintroduced into the diet. The study will focus on the four most common foods that trigger EoE: milk, egg, wheat, and soy. For the initial food introduction, the subjects will add one serving size of the food daily for 12 weeks. After 12 weeks, the subjects will have a 2nd endoscopy if the 2nd endoscopy is normal, the subjects will increase the trigger food to 2 serving sizes a day or add an additional trigger food. A 3rd endoscopy will be done if the patients increase the food amount or adds a new food at week 38 (12 weeks after adding the new food). If the subject does not increase or add new foods at week 25, the 3rd endoscopy will not be obtained. All subjects will have end of study endoscopy at week 51.

If the subjects have abnormal endoscopy or increase in symptoms, the amount of food will be reduced by 50% and repeat endoscopy will be obtained at the same time schedule-12 weeks later. (See Figure 1 and Table 1)

Screening Phase

Potential subjects will be screened using the protocol inclusion and exclusion criteria based on review of their medical records.

Parental/guardian permission (informed consent) and, if applicable, child assent, will be obtained prior to any study related procedures being performed. After consent is obtained, research blood samples will be drawn to confirm eligibility based on clinical laboratory parameters. Females of child bearing potential will have an urine pregnancy test.

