3.1.2 Food Introduction

If research subjects have a clinical response to dupilumab, they will introduce an EoE trigger food at one serving size per day. After 12 weeks, repeat EGD and symptoms score will be obtained. 12 weeks is being used as determined clinical and histologic responses can be seen at that time point in previous clinical studies¹⁸.

The foods (milk, egg, soy, and wheat) to be introduced after having caused exacerbation of their EoE by standard definitions:

- Addition of a single food lead to exacerbation of esophageal eosinophilia (increase of greater than 15 eos/hpf) or
- Removal of a single food lead to normalization of biopsy (esophageal eosinophilia showed less than 6 eos/hpf)
- AND
- History of either milk, egg, soy, or wheat induced EoE based on introduction of the food and symptoms in the last 12 months

Foods in phase 1 will be introduced as one serving size at week 13. If biopsy at week 25 are less than 6 eosinophils/HPF, the subjects will have one of 2 options

- Increase the serving size to 2 servings a day or
- Add an additional EoE trigger food

If the week 25 biopsy show 6-15 eosinophils/hpf, the diet will remain the same

If the week 25 biopsy show >15 eosinophils, the diet will decrease to ½ serving size a day

For the week 38 endoscopy with biopsy, the three scenarios are

If the biopsy show < 6 eosinophils/hpf, the three options are

- Increase the serving size to ad lib (if one food) or
- Add a 3rd EoE trigger food or
- Increase the serving size of 1st and 2nd foods to 2 serving size a day

If the biopsy shows 6-15 eosinophils/hpf, the plan is to remain at the current diet

If the biopsy show >15 eosinophils/hpf, the plan is to decrease the serving size by 50%

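### Section 3.1 cuts food for worse symptoms or an undefined abnormal endoscopy, while 3.1.2 and Table 1 use biopsy count alone, so some subjects get opposite or conflicting diet instructions

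*Combined protocol and SAP*

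**What the plan says.** **Section 3.1 (General Schema of Study Design)** works with two states. For advancing: "if the 2nd endoscopy is normal, the subjects will increase the trigger food to 2 serving sizes a day or add an additional trigger food". For cutting back: "If the subjects have abnormal endoscopy or increase in symptoms, the amount of food will be reduced by 50" per cent, with a repeat endoscopy 12 weeks later. Neither *normal* nor *abnormal* is defined there, and no size, instrument or reference visit is given for a symptom increase.

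**Section 3.1.2 (Food Introduction)** works with three histology bands and no symptom condition.
- Week 25, lowest band: "If biopsy at week 25 are less than 6 eosinophils/HPF, the subjects will have one of 2 options" (two servings, or another trigger food). The middle band is held: "If the week 25 biopsy show 6-15 eosinophils/hpf, the diet will remain the same". For the highest band the amount is cut: "If the week 25 biopsy show >15 eosinophils, the diet will decrease to ½ serving size a day".
- Week 38, lowest band: "If the biopsy show < 6 eosinophils/hpf, the three options are" (each one increases exposure). The middle band is again held: "If the biopsy shows 6-15 eosinophils/hpf, the plan is to remain at the current diet". For the highest band the amount is again cut: "If the biopsy show >15 eosinophils/hpf, the plan is to decrease the serving size by 50" per cent.

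The text under **Table 1** repeats the 3.1.2 rule. Table 1 also schedules a symptom score at every visit from 1 to 16, so symptoms are known at each diet decision.

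The **synopsis** (Study Phases) makes the second food conditional on normal biopsies, again without a cut-off.

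**The concern.** The study asks whether trigger foods can be eaten on dupilumab without a flare, so the amount of food is the exposure under test. If two sections give different instructions for the same biopsy and symptom result, that amount depends partly on which section staff follow. The week-38 and week-51 histology, symptom and quality-of-life results would then mix exposures for a reason that is neither planned nor recorded.

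There is also a subject-protection side. Section 7.10.2.3 names symptom exacerbation as the main risk of food introduction, yet a subject with worse symptoms could be escalated under one section and cut back under another.

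**Working it through.** No power or alpha figure is involved. The check sets the two rules side by side for each combination of biopsy band and symptom change.

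**Step 1: what *abnormal* could mean.** The documents support two cut-offs.
- Section 3.1.2 ties normalization of a biopsy to fewer than 6 eos/hpf, which makes 6-15 abnormal.
- Section 5.6 treats 15 eos/hpf as abnormal, and the synopsis calls biopsies active above 15. On these, counts of 6-14 are not abnormal.

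**Step 2: compare the rules.**

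| Biopsy (eos/hpf) | Symptoms | 3.1, abnormal = 6 or more | 3.1, abnormal = about 15 | 3.1.2 and Table 1 | Result |
|---|---|---|---|---|---|
| <6 | not worse | advance | advance | advance | agree |
| <6 | worse | reduce | reduce | advance | opposite |
| 6-15 | worse | reduce | reduce | keep | conflict |
| 6-15 | not worse | reduce | no cut; advance if counted as normal | keep | unclear |
| >15 | either | reduce | reduce | reduce | agree |

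Rows 2 and 3 do not depend on the meaning of *abnormal*, because the symptom trigger alone produces the cut. In row 2, Section 3.1 also conflicts with itself: the normal endoscopy calls for an increase and the symptoms for a reduction.

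**Step 3: size of the gap in food amount at week 25, starting from one serving.**
- Reduce: 1 × 0.5 = 0.5 serving.
- Keep: 1 serving. Gap to reduce: 1 / 0.5 = 2-fold.
- Advance by amount: 2 servings. Gap to reduce: 2 / 0.5 = 4-fold. The alternative form of advance is a second food.

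**Step 4: knock-on for the week-38 endoscopy.** Section 3.1 orders a repeat endoscopy 12 weeks after a cut. It also says the third endoscopy is not obtained if food was neither increased nor added at week 25. A subject cut back at week 25 meets both sentences. A subject at 6-15 who is kept on the same diet has no week-38 endoscopy under 3.1; the same subject, if cut back, is due one under the repeat-endoscopy sentence. So the diet rule chosen can decide whether week-38 data exist.

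**Step 5: how many subjects.** Section 5.6 expects 64% of 30 to be evaluable: 0.64 × 30 = 19.2, about 19. Each subject is then 1/19 = 5.3% of the analysis. The documents give no expected share at 6-15 eos/hpf after food introduction and no expected rate of symptom worsening, so the count in rows 2 to 4 cannot be derived.

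**The case against.** **Section 3.1 is only a general schema and points to Table 1.** On biopsy bands, staff then have one detailed rule, stated twice. This carries some weight for row 4. It does not settle rows 2 and 3: the symptom trigger appears only in 3.1, the text under Table 1 lacks it, and nothing says which section governs.

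**The symptom rule may be an addition to 3.1.2.** Section 3.1.2 does not say symptoms are to be ignored, and Section 7.10.1 describes monitoring visits for worsening symptoms. That reading is possible but nowhere stated, and 3.1.2 still offers only increases below 6. Figure 1, which 3.1 also cites, was not available to this review; a symptom branch there would help but would still differ from the Table 1 text.

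**Exposure after week 25 varies by design.** This stands. Subjects below 6 choose among options, including ad lib intake at week 38, and Section 5.1.9 has a daily diary of the amount eaten. A reader might infer that one cut-back rule would give a single defined exposure, or that the amount eaten is lost. The documents support neither. What can be removed is the variation caused by inconsistent instructions.

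**The primary endpoint may be untouched.** Also fair. If its two endoscopies are weeks 12 and 25, diet decisions taken at week 25 or later cannot affect it. Only if they are weeks 25 and 38 does the problem reach it.

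**Conclusion.** The rules cannot all be followed as written. The conflict is outright for subjects with worse symptoms: opposite instructions below 6 eos/hpf (four-fold in amount from one serving, or a second food) and reduce against keep at 6-15 (two-fold). This holds under either meaning of *abnormal*.

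A reader might infer that everyone at 6-15 gets opposite instructions. The text does not support that. With worse symptoms the clash is reduce against keep. Without worse symptoms it turns on an undefined word for which the documents support both a cut-off of 6 and one of 15.

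No count of affected subjects is claimed, because any percentage would be a guess. The sample-size figures in 5.6 are unaffected. The consequences fall on the week-38 and week-51 secondary results, on whether a week-38 endoscopy takes place, and on whether a subject with worse symptoms is escalated. The conclusion rests on the written text, without Figure 1.

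**What to change.** 1. Reconcile the synopsis, 3.1, 3.1.2 and the text under Table 1 (and check Figure 1) into one decision table keyed on histology band and symptom change, worded identically wherever it appears.
2. Define *normal* and *abnormal* by eosinophil count, including where a count of exactly 15 falls.
3. Define *increase in symptoms*: which of the two symptom instruments, what change, and against which visit. Section 5.4.3.6 defines improvement only.
4. Align the week-38 endoscopy rule, so that it is clear whether subjects who are cut back or kept on the same diet have one.
5. State in Section 5.4.3 that week-38 and week-51 results will also be shown by food amount eaten, taken from the existing diet diary.

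Which diet rule applies in each cell is a clinical decision for the investigator. The cost is protocol wording and one descriptive table, with no new data collection.

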3.1.1 Disease Control

At the initial phase, research subjects will start on dupilumab based on the dosage used in the 2 phase 3 clinical trials. Based on previous data, patients respond within 12 weeks, therefore, a baseline endoscopy showing a clinical and histologic response will be obtained at week 12. If patients show clinical response with dupilumab as defined as esophagus biopsy with less than 6 eosinophils/hpf. If the biopsy does not improve such that eosinophil count is still greater than 15 eosinophils/hpf, the subject will exit the study. If the biopsy is between 6-15 eosinophils/hpf, the subject will be treated for an additional 12 weeks on dupilumab. If the biopsy is still not less than six eosinophils/hpf, the subject will exit the study. If the subjects have biopsy have less than six eosinophils/hpf (FDA definition of remission), the subjects will advance to food introduction phase of the study.

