6. Narrow caliber esophagus defined as the inability to pass a 9.5 mm endoscopy into the esophagus
7. IgE mediated reaction to food (milk, egg, soy, or wheat) being introduced in the last 12 months
8. No change in the dose of swallowed steroids for Eosinophilic Esophagitis for 2 months prior to starting the study and throughout the study (their current standard of care EoE treatments)

Number Of Subjects 30 patients

Study Duration Each subject's participation will last 52 weeks

Study Phases 1) The first phase is the initial disease control in patients with

Disease Control Eosinophilic Esophagitis. Subjects will be treated with dupilumab for 12 weeks (per current proposed dosing in EoE clinical trials)

Food introduction

-
- a. At the end of the 12 weeks, subjects will have endoscopy showing resolution of EoE
- 2) **Food introduction:** If subjects do not have active esophageal biopsies (defined by greater than 15 eos/hpf) and have decreased symptoms per EoE symptom score, the subjects will continue dupilumab at current dosing regimen
- a. They will introduce one food (per food introduction guideline) for 12 weeks, then, upper endoscopy with biopsy will be done to examine EoE disease status
 - b. If biopsies are normal, second food can be added, final endoscopy will be performed at week 51 to determine the stability of food introduction on dupilumab
 - i. If a 3rd food was shown to be causative, it can be added at week 38.

Efficacy Evaluations	Esophageal Biopsy (Eosinophils/high power field) Esophageal Symptom Scores
Pharmacokinetic Evaluations	Not applicable
Safety Evaluations	Safety measures including symptom score, adverse events from dupilumab and endoscopies will be collected at each visit.
Statistical And Analytic Plan	
The primary statistical efficacy endpoint will be tested using a Paired T-test on the change in peak eosinophil counts on esophageal biopsies between 1st and 2nd endoscopy after food introduction in the same patient.
 
If peak eosinophil counts do not satisfy the assumption of normality, instead the Wilcoxon Signed-Rank test will be used for the primary.

DATA AND SAFETY MONITORING PLAN	The principal investigator will be responsible for the safety and monitoring of the study and data validation of the study.

TABLE 1: SCHEDULE OF STUDY PROCEDURES

Study Phase	Disease Control				Food introduction												Follow-up
	1	2	3	4	5	6*	7*	8	9	10*	11*	12	13	14*	15*	16	17

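### The synopsis and section 3.1.1 give incompatible week-12 rules for subjects at 6–15 eos/hpf, and the extension in 3.1.1 is not mapped to the visit schedule

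*Combined protocol and SAP*

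**What the plan says.** **Synopsis, Study Phases.** The condition for food introduction after the week-12 endoscopy is: "If subjects do not have active esophageal biopsies (defined by greater than 15 eos/hpf) and have decreased symptoms per EoE symptom score". A subject who meets it stays on dupilumab and introduces one food for 12 weeks. There is no extension branch.

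**Section 3.1.1.** Below 6 eos/hpf the subject goes forward: "less than six eosinophils/hpf (FDA definition of remission), the subjects will advance to food introduction phase of the study". Above 15 the subject leaves. For the band between: "If the biopsy is between 6-15 eosinophils/hpf, the subject will be treated for an additional 12 weeks on dupilumab", followed by "If the biopsy is still not less than six eosinophils/hpf, the subject will exit the study".

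**Section 3.1.** "If disease is controlled based on histologic and symptom control at week 12 endoscopy, patients will start on EoE trigger food". No count is attached to the word controlled.

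**Section 3.1.2.** "If research subjects have a clinical response to dupilumab, they will introduce an EoE trigger food at one serving size per day". Section 3.1.1 defines that response as a count below 6. Section 3.1.2 also fixes the first serving at week 13 and ties the first diet decision to a week-25 biopsy.

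**Duration and exit.** The synopsis states that each subject's "participation will last 52 weeks". Section 3.3.1 repeats this as 51 weeks of treatment plus 1 of follow-up, and has subjects without a response to dupilumab leave at week 13.

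**Visits.** In Table 1 and sections 4.1–4.2, visit 4 (week 12, endoscopy) is followed by visit 5 (week 13), where section 4.2.1 lists a new food.

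**Endoscopy status.** Section 7.10.2.2 counts only the first endoscopy as research. It treats the others as standard of care because foods are being introduced.

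**The concern.** The two rules lead to opposite actions on the same result, and the action is whether a subject is given a food known to trigger that subject's disease. The synopsis and section 3.1 also make symptom improvement a condition, while the sentence in 3.1.1 that admits subjects to food names histology only.

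If 3.1.1 is the operative text, its extension lacks what is needed to run it: a visit for the repeat biopsy, an exit time for those who fail, later diet decisions, and a status for a second endoscopy done before any food.

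There is a smaller consequence for analysis. An extended subject has two pre-food biopsies, and the primary endpoint (section 5.3.1) names no week or visit. Section 3.1.1 does not settle which one counts: "a baseline endoscopy showing a clinical and histologic response will be obtained at week 12" points to the first biopsy by its timing and to the requalifying one by its description.

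**Working it through.** **1. Same subject, two rules.** Take a week-12 peak of 10 eos/hpf with decreased symptoms.

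| Text | Week-12 action | Next step |
|---|---|---|
| Synopsis | 10 is not above 15, so food starts | Endoscopy after 12 weeks of food |
| Section 3.1.1 | 10 lies in 6–15, so dupilumab continues without food | Repeat biopsy; food if below 6, otherwise exit |

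The rules agree on histology below 6 and above 15. They part only in the band. Section 3.1.2 follows the below-6 rule, and section 5.6 builds its evaluable number from below-6 rates: the mean of 67% and 59.5% is 63.25%, and 30 × 0.6325 = 19.0, the stated 19.

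**2. The plan's 52 weeks.** In Table 1, food starts 1 week after an endoscopy and the next endoscopy comes 12 weeks later. From the week-12 endoscopy, food/endoscopy falls at 13/25, 26/38 and 39/51, and follow-up is at week 52. The stated duration is reproduced, without the extension.

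**3. Adding the extension.**

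- Repeat biopsy at 12 + 12 = week 24: cycles at 25/37, 38/50 and 51/63, end at week 64 (63 on treatment).
- Repeat biopsy at the existing week-25 visit: cycles at 26/38, 39/51 and 52/64, end at week 65.
- Repeat biopsy at week 25 with 52 weeks kept: cycles at 26/38 and 39/51 only, so two of three.
- Failed extension: exit at about week 24–25, against week 13 in section 3.3.1.

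The two-cycle path uses existing visits: drug is dispensed at visits 5 and 6, there is an endoscopy at visit 8 (week 25), food at visit 9 (week 26), and endoscopies at weeks 38 and 51. But visit 5 lists a new food, the week-25 diet rules presuppose that a food is being eaten, and Table 1 labels the week-25 endoscopy as standard of care for food introduction. None of these fits a subject who has had no food.

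**4. How many subjects.** Phase 3 gives 64% below 15 at week 12 (section 1.3.1.1). The below-6 rates quoted are 59.5% and 67% (section 5.6) and 58.8% and 65.2% (section 7.10.3). Both phase 2 below-6 rates exceed the phase 3 below-15 rate, so subtraction across these sources cannot fix the band. The site's own series has 22 of 26 below 6 (section 1.3.1.1), so at most 4 of 26 were at 6–15. If that series carried over, the range would be 0 to 30 × 4/26 = 4.6 subjects.

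**5. Effect on the analysis.** At the plan's effect size of 0.7 (two-sided 0.05 assumed, since sidedness is not stated), paired t-test power is 82% at n = 19 and 84% at n = 20, so one subject is worth about 2 points. For an extended subject who requalifies, the first biopsy is 6–15 and the repeat 0–5. They differ by 6 − 5 = 1 to 15 − 0 = 15. On a mean of 20 subjects that is 1/20 = 0.05 to 15/20 = 0.75 per such subject, against a planned difference of 11.

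**The case against.** **The synopsis is a summary, and 3.1.1, 3.1.2 and 5.6 agree on below 6.** That describes the balance of the text, but no passage says which prevails. The synopsis is not obvious shorthand for below 6 either: it expects the week-12 endoscopy to show resolution, and the plan's secondary endpoints define resolution as below 15, separately from remission at below 6.

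**The extension fits on existing visits.** This stands in part. Three food cycles are not compulsory, section 5.1.6 allows six endoscopies against four scheduled, and section 4.4 permits unscheduled visits. A reader might infer that the extension cannot be fitted into 52 weeks; the two-cycle path shows that it can. What remains is that no passage assigns it to visits, and the week-13 exit is wrong for a failed extension on any mapping. Figure 1 is not shown and might contain the branch, but the text would still conflict.

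**The plan tolerates trigger food at 6–15.** Section 3.1.2 leaves the diet unchanged at 6–15 once food has started. So the documents do not support reading the synopsis rule as unacceptable in itself. The problem is two entry rules. Similarly, a subject starting food at 6–15 has no below-6 remission to maintain, but the companion endpoint of maintained resolution (below 15) still applies to nearly all such subjects.

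**Section 4.6.** A reader might cite its lack-of-response definition (above 15 at week 12) as a further contradiction. It agrees with the week-12 exit in 3.1.1.

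**Conclusion.** The concern holds for the entry rule and for the unmapped extension. The entry-rule conflict rests on text alone and needs no assumption. The schedule figures (64–65 weeks for three cycles, two cycles within 52, exit at about week 24–25) assume only that Table 1's spacing carries over to an extended subject. A repeat pre-food endoscopy also falls outside section 7.10.2.2.

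The number of subjects affected is not known. The range of 0 to 4.6 of 30 rests on a small retrospective site series of patients treated mostly for other indications. A reader might want a sharper rate, or a probability that at least one subject meets the conflict, but the quoted trial rates are not mutually consistent enough to give one.

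A reader might also infer a sample-size error or a need to redefine the primary endpoint for everyone. Neither follows. The stated 19 evaluable subjects reproduce, and if the group is small, as is likely, power and the primary mean hardly move. The endpoint issue that arises here is confined to naming the pre-food biopsy for extended subjects.

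**What to change.** Reconcile the synopsis, sections 3.1, 3.1.1, 3.1.2, 3.3.1 and 7.10.2.2, and Table 1 to a single entry rule for the food phase, covering both histology and symptoms. Which rule applies is for the sponsor to decide.

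If the extension is kept, also:

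- map it to named visits, including the repeat endoscopy and drug dispensing;
- give the exit time for a subject who fails it;
- state either the number of food cycles within 52 weeks or a longer total duration, and when the later diet decisions fall;
- state whether the repeat pre-food endoscopy is research or standard of care;
- state that the pre-food value for such a subject is the last biopsy before the first serving.

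The cost is a wording amendment and one sentence in the analysis section. Keeping two cycles within 52 weeks needs no extra drug. Keeping three means 12–13 more weeks of drug supply and participation, plus one more endoscopy (five, within the limit of six), for the few subjects concerned.
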